## 1. Principal goal of the study.

The principal goal of this study is to improve the efficacy of deep brain stimulation (DBS) as treatment for disabling action tremor of the arms, the most common form of involuntary movement disorder in both younger and more elderly adults (1). With increasing severity, action tremor impairs many important activities of daily living, can render affected individuals unable to work, and can lead to complete dependence on assistance from others. Efficacy of medical treatment for this condition is very limited and often unsuccessful. In severe cases DBS is the only potentially effective treatment (2). DBS of the thalamic nucleus Ventralis Intermedius (VIM) has traditionally been used, but the posterior subthalamic area (PSA) has been suggested recently as a better target, leading to more complete and sustained tremor-suppression. More complex types of action tremor have also been successfully treated using the PSA. However, controlled and comparative studies of the two targets are lacking, and have been called for by world-leading tremor experts (2, 3).

The Departments of Neurology and Neurosurgery at Oslo University Hospital (OUH), together with the corresponding departments at St Olav's Hospital in Trondheim, have been given the national task to provide DBS treatment to the Norwegian population. From the outset, this study was therefore planned as a multi-center study, with both OUH and St Olav's hospital as including centers, and with international collaboration with a world leading German DBS center (University Clinic Wuerzburg/headed by professor [name]) - to perform the first double-blind, randomized, controlled , comparative study of VIM- versus PSA-DBS in disabling action tremor. However, St Olavs Hospital withdrew their consent to participate before inclusion was started.

Therefore, Oslo University Hospital has been the only center including patients since inclusion was started in April 2014. Inclusion was closed in December 2018, with 45 patients included. The collaboration also includes the Western Health Region, so that patients will be recruited from all health-regions of Norway.

Clinical efficacy and safety will be related to precise stimulus location, assessed by fusion of preoperative MRIand postoperative CT. Neuropsychological testing will elucidate whether cognitive functions are altered.

This study will allow us to determine which DBS target provides the best and most sustained suppression of action tremors. Improved efficacy will greatly enhance the function and well-being of many patients, improve their work-participation and reduce their need for assistance in daily-life activities, and thus increase the cost-effectiveness of this resource-demanding therapy.

# 2. Aspects relating to the research project

## 2.1. Background and status of knowledge

Tremor is defined as rhythmic and oscillating involuntary movements of a body part. *Action tremor* occurs when a body part is activated, and is clinically most frequently seen in Essential (idiopathic) Tremor (ET), with an overall prevalence of 0.9 %, and of 4.6 % in people over 65 years (1). But it can also be the most disabling symptom in many other neurological diseases such as dystonia, multiple sclerosis (MS), advanced Parkinson's disease (PD), and some spino-cerebellar ataxias.

## Relevant physiology and anatomy

The basic *normal* physiological mechanisms that underlie tremor are central neurogenic oscillations, spinal and supraspinal reflex oscillations, and peripheral mechanical oscillations. *Central neurogenic pathological tremors* emerge from disruptions of central neural networks involving pathways from spinal cord to cerebellum, from cerebellum via brainstem to thalamus, and thalamo-cortical loops via the basal ganglia. Simultaneous recordings of EMG (electromyography), EEG (electroencephalography), and MEG (magnetoencephalography) have demonstrated the involvement of ipsilateral cerebellum, contralateral thalamus and sensorimotor cortex in ET, Parkinson, and several other tremor types. Thus, the cerebello-thalamo-cortical pathway is probably involved in all tremors (4). The exact mechanisms that disrupt these pathways and produce pathological oscillations in the various tremor conditions remain, however, largely unknown. The cerebello-thalamic tract originates from the cerebellar nuclei (dentate, emboliform and globose), ascends and crosses in the pons and enters the *red nucleus* (RN). Most fibers project further to the ventral thalamic nuclei - oralis (VO) and intermedius (VIM). The RN lies in the mesencephalon, medial and ventral to the subthalamic nucleus (STN). The *posterior subthalamic* area (PSA) is the region inferior to VO and VIM, dorsal and posterior to STN, and lateral to RN. Its principal components are the nucleus called Zona Incerta (ZI) and the fibre bundle called the prelemniscal radiation (RaPrl). The important descending motor pathway (pyramidal tract) lies laterally and the important ascending sensory pathway (medial lemniscus) lies posteriorly to PSA. Whereas STN and RN are visible on standard T2-weighted MRI-scans, PSA is only indirectly defined by these surrounding structures. A study using diffusion-tensor imaging (DTI) and fiber tracking has, however, shown that DTI can potentially differentiate between the fiber tracts passing through this area, and thus can greatly improve assessment of the anatomical structures affected by the current from an implanted DBS electrode (11).

#### Classification and differential diagnosis of action tremor disorders

This can be difficult, since with rare exceptions there are no confirmative diagnostic tests or biomarkers for the primary tremor forms. Differential diagnosis of primary action tremor forms such as ET, Dystonic tremor (DT) and Cerebellar tremor (CbT), therefore relies mainly on clinical examination and the exclusion of underlying diseases causing secondary action tremors (such as PD and MS) by supplementary imaging and other lab tests. Action tremor is divided into *postural* (when a position is maintained), or *kinetic* (when a movement is made). Other neurological findings (dystonia, cerebellar, pyramidal, parkinsonian, neuropathic signs), and systemic signs must be assessed. Age at onset, associated disease, medication history/response, response to alcohol, possible drug abuse and family history of neurological disease (especially tremor) must be assessed. - ET. Mainly a bilateral, largely symmetric postural or kinetic tremor involving the hands and forearms. Additional or (rarely) isolated head tremor may occur, but no abnormal posturing. Other causes of primary or secondary tremor forms must be excluded (5).

- DT. Strongly supportive of DT are other signs of dystonia (abnormal posturing and frank, involuntary dystonic movements). Suggestible, softer signs are asymmetrical and irregular or jerky limb tremor, atypical rest tremor, and position-or task-specific tremor.

- CbT. For this diagnosis, there must be a pure or dominant intention tremor of the extremities, unior bilateral, with a frequency mainly below 5 Hz. Postural tremor may be present, but no rest tremor. If only postural tremor is present, other clear cerebellar signs must be present to classify the tremor as cerebellar. So-called titubation of the head or trunk is a slow-frequency oscillation in the erect positon that is also thought to be of cerebellar origin.

- Holmes tremor. Rest- and intention tremor, +/- postural, frequency usually < 5 Hz, often associated with a lesion of the brain stem, cerebellum or thalamus

- Neuropathic tremor. Postural or kinetic tremor of limb(s) affected by a peripheral neuropathy.

#### Supplementary diagnostic workup

- MRI is obligatory in all tremor cases to show/exclude tremor-causing lesions such as infarcts, MS plaques or other inflammatory diseases, cerebellar atrophy, or atrophy or pathological signal changes along the cerebello-thalamo-cortical circuits, including the basal ganglia.

- DAT-scan/I-FP-CIT SPECT of the DopAmine Transporter (DAT) shows reduced binding in the striatum in PD and other degenerative parkinsonisms, but not in ET, DT or CbT. - Laboratory tests. Blood (+/- CSF and urine) to exclude hyperthyreosis, electrolyte disturbances, metals (iron, copper), hyper/hypoglycemia, vitamin B12 deficiency, hepatic or kidney diseases.

## Treatment of primary action tremor disorders

**I. Medical treatment.** As neither the molecular or neurotransmitter deficits or the mechanisms of the pathological oscillations are known, medications used are only symptomatic. The two most commonly used drugs for ET, the non-selective beta-blocker propranolol and the anticonvulsant primidone, both received a level A recommendation of efficacy by the American Academy of Neurology in 2005. This was based on mostly small and short-term studies (3-6 weeks), showing an average tremor reduction of about 50-60% in about 50% of patients (2). No controlled long-term studies have been done, but open-label studies indicate development of tolerance and reduced effect in 10-15%. Level B evidence of a probable effect has been given to other beta-blockers (atenolol, sotalol) and the antiepileptics alprazolam, topiramate and gabapentin. None of these has been shown to be more efficaceous than propranolol or primidone (2). Unfortunately, among the many drugs tested, even those with established efficacy for ET provide only partial relief in a subgroup of patients. There have been no systematic studies for other tremors like dystonic or cerebellar tremors (4). Thus, for these patients no medications with established efficacy exist, except intramuscular botulinum toxin injections for dystonic head tremor (2).

[figure not shown]
#### **II. Deep brain stimulation (DBS)**

**i.** Stimulation of VIM. DBS of the Nucleus Ventralis Intermedius of the thalamus (VIM) has long been available, and VIM has been considered the target of choice for patients with disabling action tremor at most centers, including ours. Open-label, mostly short-term studies of VIM-DBS in ET have reported up to 80-90% reduction of action tremor, but long-term clinical experience and studies show that gradual loss of tremor control over months and years occurs in many patients (2,6). Masked raters were not used (2), except for one study (7). Several studies did not differentiate between efficacy on postural versus kinetic tremor. Of those that did, 2 of 3 showed a reduced efficacy on kinetic tremor in the long-term (6,8). This problem, termed "development of tolerance" to the stimulation, is emphasized in recent reviews (2,3) and clearly limits the functional long-term benefit of VIM-DBS. Whether this is due to tolerance to the stimulation, progression of the underlying disease process, or suboptimal electrode placement is under debate. Although reduced tremor control often can be corrected by increasing the current, this effect is only temporary or leads to intolerable side-effects. VIM-DBS is also limited by being less effective on proximal tremor, which is often the most invalidizing symptom.

Because VIM cannot be seen on MRI or mapped using microelectrode recordings, targeting it employs the use of standard stereotaxic coordinates. The definition of these varies between centers. They are defined in relation to the intercommissural line (ICL) between anterior and posterior commissures. Final placement of the electrode is decided only after peroperative clinical testing of effect on tremor and side effects in the awake patient. Thus, the cooperability of the patient and the skills of the neurologist performing peroperative testing are crucial. Bilateral VIM-stimulation is associated with a relatively high rate of side effects. In a meta-analysis of 430 patients, 19 % had paresthesias, 9 % dysarthria, 7 % headache and 6 % unsteadiness or gait difficulties. Therefore, many centers offer only unilateral stimulation to most patients even if they have bilateral tremor. **ii. Stimulation of PSA.** The limitations of VIM-stimulation have led to a renewed interest in exploring the PSA as an alternative. Open label case series from several centers indicate better results from PSA-DBS than VIM-DBS (9,10,11,12), particularly in reducing kinetic tremor, including proximal arm tremor and intention tremor. The targeted area within the PSA varies

among centers. Kitagawa et al published a dramatic response to PSA-DBS in two patients with severe proximal arm tremor, one with ET and one with DT (13) and similar results in 8 patients with ET and proximal arm tremor (9). Average tremor reduction was 81%, sustained during median 22 months of follow-up, with low current consumption. Comparison of stimulation efficacy for electrodes in VIM versus PSA favoured the latter. Stimulation in the Zona Incerta (ZI) or the prelemniscal radiation (Raprl) were both effective, and side-effects were reported to be mild and transient. Plaha et al (11) reported results from blinded 1-year follow-up of bilateral stimulation of the caudal ZI in 5 patients with PD tremor, and 13 patients with action tremors from a range of diseases (ET, MS, CbT, DT, Holmes tremor). The target was slightly lateral to that of Murata et al (for comparison, see ref 11). Average improvement of postural/action tremor was 88% and of rest tremor 95%. In the MS-patients, both severe proximal arm tremor, truncal ataxia and severe headand-neck tremor improved. There was no significant decline of clinical efficacy or significant change in stimulation parameters during serial follow-ups, but some side-effects were seen in a few patients due to misplaced electrodes or edema. Blomstedt et al reported results of PSA-DBS in 21 patients with ET (most unilateral), achieving on average 95% tremor reduction and 87% functional improvement in the contralateral arm (12). Transient, mild expressive dysphasia was observed in eight patients. In summary, the most frequent side-effects reported in PSA-DBS series are paresthesias, dysarthria, dysequilibrium and blurred vision, and thus similar to those observed with VIM-DBS, but are consistently reported to be mild and transient in almost all patients. No controlled comparison of efficacy and safety between the two targets have been reported so far. With respect to the ICL, the targets used in the above studies were 10-14 mm lateral, 6-7.5 mm posterior to midpoint, and 2-4 mm inferior. Few authors have studied different targets in the same patients. Herzog et al compared stimulating with the upper electrode contacts the thalamic level, and with the lower contacts 1.5mm below the ICL in 21 patients with ETor MS-tremor. The results favoured the contacts below the ICL (14).

In 2010, Coenen et al presented their use of DTI and fiber tracking to determine the exact location of the most effective electrode contact placed in the subthalamic area in a unilateral PD tremor patient. They concluded that effective stimulation was achieved by a contact that stimulated the dentato-rubro-thalamic tract (DRT) as this crosses the subthalamic area (15). In 2011 the same group published successful DBS in a patient with head-tremor, using visualization of the DRT by DTI-MRI for direct targeting (16, Figure 1).

**Figure 1.** Shows DBS electrode positions in relation to fiber tracts in the thalamic and subthalamic area in a patient with tremor, using helical CT merged with diffusion tension MRI/ fiber tracking. (STN= subthalamic nucleus, RN= red nucleus, THA= thalamus, DN= dentate nucleus, scp= superior cerebellar peduncle, stp= superior thalamic radiation) From Coenen et al, Acta Neurochir 2011 (ref.16)

**Fluoro-Deoxy-Glucose Positron Emission Tomography (FDG-PET) and Neuropsychological assessment.** FDG-PET was used in a recent study to define a metabolic pattern of PD tremor characterized by covarying increases in the activity of the cerebellum/dentate nucleus and primary motor cortex, and, to a lesser degree, the caudate/putamen. VIM-DBS resulted in consistent reductions in pattern expression. The findings suggest that PD tremor is mediated by a distinct metabolic network, involving primarily cerebello-thalamo-cortical pathways in which effective reduction of activity is associated with significant diminution of tremor (17). No similar study has so far assessed this in other tremor forms, or after PSA-DBS. We therefore wanted to perform FDG-PET at baseline and at 1 year of DBS, but we could not manage the costs of this procedure, and it was therefore omitted.

Possible impact on cognitive function has not been assessed in published studies of PSA-DBS. It cannot be excluded, however, that PSA-DBS or VIM-DBS could have an impact on some aspects of cognitive function. We will therefore perform a standard neuropsychological test battery in all patients before and at 1-year follow-up.

## 2.2. Approaches, hypotheses and choice of method

To overcome the limitations of today's standard method of treating severe action tremors with VIM-DBS, we will now collaborate with one of the world's leading DBS experts ([name], Germany), to perform the first double-blind, randomized, controlled and comparative study of VIM-DBS versus PSA-DBS in patients with disabling action tremor. This will entail an interdisciplinary approach that combines cutting edge neurosurgical intervention, neurophysiological manipulation, brain imaging, and neurological and neuropsychiatric assessment. In combination, these methods will provide novel insight into the design of DBS for action tremor, and help provide a platform in Norway and internationally for making similar advances in the use of DBS as a therapeutic tool for other neurological disorders.

We will implant one quadripolar (or octapolar) electrode so that it covers both targets on one side, unilaterally or bilaterally as indicated clinically. The efficacy of stimulating each target will be studied in individual patients and between patient groups in a cross-over design, in two consecutive 3-month periods, by the use of validated tremor scores. Further continuous stimulation of the most effective target in each patient will be evaluated after another 6 months. This will provide unbiased efficacy-data about the two targets, both within each patient, and between patient groups. Stimulation efficacy will also be evaluated in relation to the exact target localization, defined by merging post-op helical CT scan (shows the four electrode contacts), with pre-op MRI (the MRI protocol includes DTI uptake for fiber tracking.) Such high-resolution correlation data has to date only been published in a few action tremor patients world-wide, and will add extremely important new data to aid DBS targeting in the future. Since little is known about whether cognitive functions are altered by the disease or the treatment, we will perform neuropsychological testing before and after effective DBS treatment.

## I. Study overview.

- Study design: Single-center, prospective, randomized, double-blind. Cross-over.

- Number of patients to be included: Minimum 44.

- Inclusion criteria: Patients of both genders aged 18 – 80 years. Min 5-yr duration chronic action tremor of upper limb(s), w/ or w/out tremor of head/neck, trunk, lower limbs, who have insufficient relief from adequate trials of recommended medications. The arm tremor must be so severe that it interferes with the patient's work performance or activities of daily living, such as drinking/eating, dressing/hygiene, and/or writing. Clinical diagnosis (according to criteria defined by the Consensus Statement of the Movement Disorders Society (5)) include ET, DT, CbT- idiopathic or secondary (to e.g.MS or SCA), or severe PD tremor (who are not eligible for DBS of the subthalamic nucleus). A new clinical classification of tremor syndromes published in 2018 will also be used to support/update the clinical classification of the study population (18).

- Exclusion criteria: Brain MRI showing so marked general atrophy, or supra-tentorial white matter changes, that the safety of the procedure is affected. Co-morbidity of dementia or other severe neuropsychiatric disorder (major depression or anxiety disorder, active/recent psychosis, drug or other substance abuse). Increased risk of bleeding, cancer at advanced/not stabilized stage, other co-morbidity with short life expectancy. Other surgical contraindications.

- Identification of the surgical target: The quadripolar electrode will be placed so that each target (VIM and PSA) is covered by at least one of four electrode contacts. The targets will be found using

preoperative MRI (3 Tesla) merged with helical/3D CT, according to predefined coordinates, refined by relation to neighboring MRI-visible structures (STN and RN). Electrode trajectories will be defined to avoid cerebral sulci, vessels and ventricles.

- Primary endpoints: 1) The difference in the change from baseline to the end of each of the two 3month cross-over periods in *the objectively observed tremor of the contralateral upper limb(s)*, as evaluated by items 5 (right)/6 (left),10 (for dominant hand only), and 11-14, in the Fahn-Tolosa-Marin (FTM)-score (19), with VIM- versus PSA-stimulation. *Functional disability of arm tremor* (items 16-21) is also part of the primary endpoint evaluation.

2) The difference in the change from baseline to the end of each of the two 3-month cross-over periods in the items scoring tremor of face/tongue/voice/trunk/lower limb(s), with VIM- versus PSA-stimulation.

The exact brain area stimulated in each patient will be radiologically evaluated by the pre-op MRI merged with a post-op helical CT-scan. These images are exported via CD's to the soft-ware SureTune (Medtronic), to show the localization of the implanted electrodes (and the active contacts used) on the patient's brain anatomy. This work is done using the Visual Lab portifolio developed at the University Clinic Wuerzburg by [name] and [name] (see 2.3.), and is supervised by them.

- Secondary endpoints: 1) Change from baseline to 1-yr, with stimulation at the most optimal of 4 electrode contacts of each patient (selected after the second randomization period), of the total FTM-score, tremor of the upper limb(s) (same items as above) and of the items scoring tremor in the face, tongue, voice, trunk, lower limb(s). 2) Change from baseline to 1-yr of Quality of Life in Essential Tremor (QUEST) scale, and Visual Analogue Scale of Global Disease Burden as assessed by the patient. 3) Frequency and severity of adverse events (surgical complications and stimulation related side-effects), including eventual deterioration on neuropsychological testing from baseline to 1-yr of stimulation.

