vii) **Long-term, open follow-up extension.** All participating patients who complete the first year of the study will be invited to participate in an open, long-term follow-up study. Study examinations will be performed at 2 years and 3, 5, 7,5 and 10 years after the operation. The FTM-tremor score, neurological examination, the QUEST quality of life-questionnaire and the HAD-questionnaire will be performed. The TETRAS score will be performed in a subset of patients in whom this score was also obtained at baseline.

viii) **Power calculation and plan for statistical analyses,** Based on earlier research on deep brain stimulation in VIM and PSA for tremor, we assume a mean change (improvement) from baseline to the end of the two randomized 3 months treatment periods of 16 points (standard deviation SD=5) in our primary endpoint (composite FTM-tremorscore of contralateral arm). (Power calculation is done for dominant arm). We defined a clinically significant difference as 1.8 points between the two interventions. Furthermore, we assume a SD of differences of 4. When the sample size in each period is 41 and the number of subjects for each intervention is equal, this 2x2 cross-over design will have 80% power to detect a difference in mean change between interventions of 1.8 points using a paired t-test. In order to account for potential drop-out and missing data, 45 patients will be randomized.

Continuous and categorical data will be described with mean (SD) and number of observations (percentage), respectively. A basic statistical analysis of the 2x2 cross over design assumes no period (systematic difference between periods) and carry over (systematic difference between orders of received interventions) effect. We will assess period effect by comparing the mean response of the two periods using a paired t-test and carry over effect by comparing the mean response of the two orders of received interventions using an independent t-test. If the tests for period and carry over effects are non-significant, these effects are considered absent. Thus, a paired t-test of treatment difference gives an estimate of the treatment effect with 95% confidence interval and p-value.

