In addition, we will conduct a linear mixed model approach using a random intercept with maximum likelihood estimation to account for within-subject correlations and fixed effects for treatment, period, and carry-over (interaction between period and treatment). If the period and carry over effect are non-significant, we will re-estimate the mixed model omitting these terms. If the period or carry over effect is significant, we will re-estimate the mixed model analysis including respective significant terms and report treatment effect with 95% confidence interval and p-value adjusted for period or carry over effect. With no missing data or drop-outs, the t-test and mixed

model approach should give equal results. In case of missing data, drop-outs or discrepancy between the t-test and mixed model approach, the mixed model approach will be our conclusive analysis. A p-value < 0.05 is statistically significant.

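### The protocol lists two numbered primary endpoints and adds functional disability to them, but names and powers only one, so what counts as primary success is not fixed

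*Protocol*

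**What the plan says.** Section 2.2, I. Study overview, has a heading for primary endpoints in the plural. Endpoint 1 is the VIM-versus-PSA difference in change of contralateral upper-limb tremor, "as evaluated by items 5 (right)/6 (left),10 (for dominant hand only), and 11-14, in the Fahn-Tolosa-Marin (FTM)-score". The same entry then says of functional disability: "items 16-21) is also part of the primary endpoint evaluation". A second numbered endpoint follows before the secondary endpoints begin: "2) The difference in the change from baseline to the end of each of the two 3-month cross-over periods in the items scoring tremor". Its content is the difference "in the items scoring tremor of face/tongue/voice/trunk/lower limb(s), with VIM- versus PSA-stimulation".

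Section 2.2, II. Methods, viii) (power calculation and plan for statistical analyses) uses the singular: "in our primary endpoint (composite FTM-tremorscore of contralateral arm". It adds "Power calculation is done for dominant arm" and sizes the trial for that score alone: a difference of 1.8 points, an SD of differences of 4, 41 patients and 80% power with a paired t-test. The analysis text closes with one general rule: "A p-value < 0.05 is statistically significant".

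**The concern.** The two sections disagree on how many primary endpoints there are, and no later plan can satisfy both. The Study overview gives at least two, and three if functional disability has its own test. The power section gives one.

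The trial is meant to decide which target suppresses tremor better. While the number of primary endpoints is open, a reader of the results cannot tell whether superiority on non-arm tremor or on function alone would be a primary finding. Nor can the reader tell whether the stated 80% is the chance that the trial meets its primary objective.

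There is a second ambiguity inside endpoint 1. Items 16-21 could be summed into the arm score, tested separately, or used only as support. These are different outcomes, and one set of planning values cannot be presumed to fit them all.

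**Working it through.** **Inputs from the protocol (Methods, viii).** Difference δ = 1.8; SD of within-patient differences = 4; n = 41; power 80%; paired t-test; threshold 0.05. Sidedness is not stated. I assume two-sided, which reproduces the stated n.

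**1. The plan's own figure.** The noncentrality is δ/SD × √n = 1.8/4 × √41 = 0.45 × 6.403 = 2.88, on 40 degrees of freedom. The noncentral t distribution at two-sided 0.05 gives:

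| n | power |
|---|---|
| 40 | 79.3% |
| 41 | 80.3% |

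So 41 is the smallest n that reaches 80%. The figure is correct, and it spends the whole 5% on one endpoint.

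**2. If a win on any primary endpoint counts.** For k independent tests at 0.05 the familywise error is 1 − 0.95^k.

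- k = 2: 1 − 0.9025 = 9.75%
- k = 3: 1 − 0.857375 = 14.3%

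The protocol gives no correlation between endpoints, so the correlations below are assumptions. Simulation of k equally correlated paired t-tests (n = 41, 200,000 runs) gave:

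| assumed correlation | two tests | three tests |
|---|---|---|
| 0.3 | 9.6% | 13.7% |
| 0.5 | 9.2% | 12.7% |
| 0.7 | 8.4% | 11.0% |
| 0.9 | 7.0% | 8.4% |

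Every cell exceeds 5%. The three-test column applies only if items 16-21 are tested on their own.

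**3. If all primary endpoints must succeed.** Error is controlled at 5%, but the probability that all succeed cannot exceed the probability that the arm score succeeds (80.3% under the planning values). It equals that figure only if the other endpoints always succeed whenever the arm score does. The protocol gives no planning values for them, so joint power cannot be computed.

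**4. Weight of items 16-21.** Methods, i) scores each item 0-4. Six disability items can therefore add 6 × 4 = 24 points. For one arm, endpoint 1 has six items (5 or 6, 10, 11, 12, 13, 14), with a maximum of 6 × 4 = 24. If rest, postural and action tremor in item 5/6 are each scored 0-4 (my assumption), the maximum is 3 × 4 + 5 × 4 = 32. Summing in items 16-21 would widen the range by 24/24 = 100% or 24/32 = 75%. The 16-point change, the 1.8-point difference and the SD of 4 cannot be presumed to hold for both versions.

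**The case against.** The strongest reply is that the power section already settles the matter: only one endpoint is called primary there and only one is sized. Testing order and multiplicity rules are commonly left to a statistical analysis plan, and that plan is not at hand. It stands that a missing hierarchy is not in itself a finding. It does not remove the contradiction, because any analysis plan would have to depart either from the Study overview or from the power section.

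Several stronger readings are tempting, and the protocol does not support them.

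- *Each endpoint is tested at 0.05, so the error rate is 10-14%.* The protocol states a general threshold. It does not assign a test to each endpoint and does not say that any single win suffices. The 10% and 14% figures also need independence. All measures are parts of one scale in the same patients, with one designated blinded rater, so positive correlation is likely and the rate would be lower. The 14% end needs a separate test of items 16-21. Their placement inside endpoint 1 equally allows summation, which leaves two tests.
- *Adding items 16-21 invalidates the planning values.* The power section does not list the items behind its composite. Only the weaker statement holds: the values cannot be presumed to fit both versions.
- *Functional disability cannot be attributed to an arm and so does not belong.* The protocol describes these items as disability from arm tremor, stimulation may be bilateral, and each patient is their own control. A patient-level measure can validly compare the two targets.
- *The trial loses power through a multiplicity correction.* No such correction is planned. Power for the arm score at 5% remains about 80%.

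**Conclusion.** The concern holds as a contradiction within the protocol. Two numbered primary endpoints, with functional disability attached, stand against one named and powered primary endpoint, and only a general p<0.05 connects them. The sample size calculation is correct for one endpoint at two-sided 5%.

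The consequence depends on a success rule that the protocol does not state. Under an any-win rule, the false-claim rate is bounded by about 10% (two tests) or 14% (three) and falls with positive correlation, to about 7.0-9.6% or 8.4-13.7% over assumed correlations of 0.9 to 0.3. Under an all-must-win rule, error is controlled but 80% is not the chance of primary success. Neither rule makes the power statement fit the endpoint list. The role of items 16-21 in the arm score is also undefined.

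**What to change.** Reconcile the Study overview with the power section:

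- Name one primary endpoint, the VIM-PSA difference in change of the contralateral-arm FTM score. List its items explicitly: 5/6, 10 and 11-14, if the authors confirm that this is the score behind the 16 points, 1.8 points and SD of 4.
- Make functional disability (items 16-21) and non-arm tremor secondary, either tested in a pre-stated order after a significant primary result or reported as supportive.
- Inclusion closed in December 2018 (Section 1), so this changes listed outcomes late in the trial. Date it and justify it before treatment-coded results are seen.

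The cost is that a result on function or non-arm tremor alone can no longer be called a primary finding. No extra patients or procedures are needed; error stays at 5% and the 80% statement becomes true as written.

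Keeping several primary endpoints with an equal split of alpha is less practical. At 1.8 points and SD 4, 80% power would need 50 evaluable patients at 0.025 or 55 at 0.0167, and only 45 were included. With all 45 evaluable, power would be 75.5% or 70.1%; with 41, 70.8% or 64.9%.
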